## 6.2 Reported Adverse Events and Potential Risks

According to the US prescribing information (PI) for ACTOplus met® XR, there have been no clinical efficacy studies conducted with the single-tablet drug product, only pharmacokinetic bioequivalence studies have been conducted. However, two clinical studies have been conducted of co-administration of separate tablets of pioglitazone (pio) vs. placebo (pcb) as an add-on to metformin (met). The most common adverse events (AEs) seen in pio/met more commonly than pcb/met were edema (6.0% vs. 2.5% of patients) and headache (6.0% vs. 1.9%). In an uncontrolled trial comparing two different dose levels of pioglitazone, the most common AEs that were increased in 45 mg pio/met compared with 30 mg pio/met were: edema (13.9% vs. 5.8%), upper respiratory tract infection (13.5% vs. 12.4%), increased weight (6.7% vs. 2.9%), and headache (5.8% vs. 5.4%). One AE of congestive heart failure (CHF) resulting in hospitalization was observed for both doses of pio co-administered with met (1/168 on 30 mg pio/met; 1/416 on 45 mg pio/met), whereas no patients on pcb/met developed CHF. Modest weight gain was seen with both doses of pio/met (+0.9 kg 30 mg pio/met, +1.8 kg 45 mg pio/met) compared with weight loss on pcb/met (-1.4 kg).

Common AEs observed for pioglitazone monotherapy vs. placebo from two pooled studies of 16 and 26 weeks' duration were: upper respiratory tract infection (13.2% vs. 8.5%), headache (9.1% vs. 6.9%), sinusitis (6.3% vs. 4.6%), myalgia (5.4% vs. 2.7%), and pharyngitis (5.1% vs. 0.8%). For a longer pioglitazone monotherapy study (mean duration of follow-up 34.5 months) the most common AEs compared with placebo were: hypoglycemia (27.3% vs. 18.8%), edema (26.7% vs. 15.3%; reversible upon drug discontinuation), cardiac failure (8.1% vs. 6.1%), pain in extremity (6.4% vs. 5.7%), back pain (5.5% vs. 5.1%), and chest pain (5.1% vs. 5.0%). Additionally, pioglitazone monotherapy results in

significant weight gain compared with placebo, after a median of 2.7 years, pioglitazone resulted in a median +3.6 kg vs. -0.5 kg for placebo. An elevated incidence of bone fractures was observed only for women on pioglitazone compared with placebo (5.1% vs. 2.5%) after a mean follow-up of three years. Finally, post-marketing reports of macular edema (uncovered due to blurred vision or by ophthalmologic exam) in some patients has been reported.

In a meta-analysis comparing safety and effectiveness of diabetes drug therapies, Bennett *et al*, [55] analyzed hypoglycemia risk by pooling data from randomized, active-controlled studies. For combination treatment of metformin with either pioglitazone or rosiglitazone, in comparison with metformin alone, the combination of metformin with a thiazolidinedione barely increased the low hypoglycemia event frequency, 3.3%, (51/1530 patients) compared with metformin monotherapy, 2.2% (34/1543 patients). In a different set of pooled studies, a similar low hypoglycemia frequency was seen for the same combination metformin plus thiazolidinedione arm, 3.8% (32/853 patients) in comparison with the combination of metformin plus a sulphonylurea, 24.3% (198/816). When all patients treated with the combination of metformin plus thiazolidinedione in the two different set of studies were combined, the cumulative frequency of hypoglycemia remained very low, 3.5% (83/2383).

The most common AEs observed for metformin monotherapy vs. placebo were: diarrhea—most common AE drop reason (53.2% vs. 11.7%), nausea/vomiting (25.5% vs. 8.3%), flatulence (12.1% vs. 5.5%), asthenia (9.2% vs. 5.5%), indigestion (7.1% vs. 4.1%), abdominal discomfort (6.4% vs. 4.8%), and headache (5.7% vs. 4.8%). Serum vitamin B12 concentrations have been found to be lower with long-term metformin monotherapy. Pioglitazone treatment led to an increased incidence of bladder cancer in two-year carcinogenicity studies compared with placebo treatment. However, in human clinical studies the incidence of bladder cancer is slightly elevated with pioglitazone monotherapy compared with placebo, though wording on the PI indicates that there are too few events of bladder cancer to establish causality to pioglitazone.

Two serious, rare AEs are highlighted in the PI boxed warning. The first is congestive heart failure, which may be caused or exacerbated by pioglitazone. The second is lactic acidosis due to metformin accumulation in the context of another co-morbidity such as sepsis, dehydration, excess alcohol intake, hepatic or renal impairment, and acute congestive heart failure. Participants should be carefully monitored for and encouraged to report immediately any signs and symptoms of congestive heart failure or lactic acidosis after initiating study treatment. These symptoms of congestive heart failure include: excessive, rapid weight gain, dyspnea, and/or edema. Symptoms of lactic acidosis include malaise, myalgia, respiratory distress, somnolence and abdominal pain. Upon report or finding of any of these symptoms, the participant should be instructed to discontinue taking the study agent immediately and brought in for evaluation. Suspected lactic acidosis should be managed in a hospital setting.

Based on the safety profile of pioglitazone and metformin as monotherapy and as a drug combination, ACTOplus met® XR should not be used in patients with heart failure, renal impairment, liver disease, or history of or active bladder cancer. Additionally, metformin may lower vitamin B12 levels, and pioglitazone may reduce hemoglobin and/or hematocrit; thus, these should be monitored annually.

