## **5. AGENT ADMINISTRATION**

Intervention will be administered on an outpatient basis. Reported AEs and potential risks are described in Section 6.2.

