## 5.6 Dose Modification

CTCAE v4 Grade	Attribution to Study Agent	
	Unlikely/Unrelated	Possibly/Probably/Definitely Related
1	
 
No modification unless the A.E. is unacceptable to the participant or the physician feels it is in the participant's best interest medically.
 
If the A.E. may be related to dose timing, asses how the participant is dosing their study agent and if taking it at a different time of day or with a more substantial meal might help.
 
If dose modification is necessary because taking the agent with a more substantial meal did not improve the event, the participant finds it unacceptable, or the physician feels it is in the participant's best interest medically, the participant may be instructed to take the study agent every other day.
 
If none of these measures is successful and the A.E. is unacceptable to the participant or the physician feels it is in the participant's best interest medically, study agent should be discontinued. However, the participant, if willing, should still be followed per the protocol schedule of events and have all study procedures conducted.
 
	

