2	
 
No modification unless the A.E. is unacceptable to the participant or the physician feels it is in the participant's best interest medically.
 
If the A.E. may be related to dose timing, asses how the participant is dosing their study agent and if taking it at a different time of day or with a more substantial meal might help.
 
If dose modification is necessary because taking the agent with a more substantial meal did not improved the event and the participant finds it unacceptable or the physician feels it is in the participant's best interest medically, the participant may be instructed to take the study agent every other day.
 
If none of these measures is successful and the A.E. is unacceptable to the participant or the physician feels it is in the participant's best interest medically, study agent should be discontinued. However, the participant, if willing, should still be followed per the protocol schedule of events and have all study procedures conducted
 
	
 
If the A.E. may be related to dose timing, asses how the participant is dosing their study agent and if taking it at a different time of day or with a more substantial meal might help.
 
If the AE is unlikely to be related to dose timing or did not respond to taking the study agent at a different time of day or with a more substantial meal, instruct the participant to hold study agent until the AE resolves to <math>\leq</math> Grade 1 then re-start on an every-other-day dosing regimen.
 
If the AE recurs, discontinue study agent and do not re-start. However, the participant, if willing, should still be followed per the protocol schedule of events and have all study procedures conducted.
 

3	Hold study agent until consulting with the protocol's medical monitor and study chair. The medical monitor and study chair will advise whether study agent may or may not be restarted and whether a dose modification is indicated.	Discontinue study agent. Do not re-start. However, the participant, if willing, should still be followed per the protocol schedule of events and have all study procedures conducted.
4		

Hypoglycemia (The symptoms include):		
Sweating, chills and clamminess	Nervousness/shakiness/anxiety	Hunger and nausea
Irritability/impatience/confusion	Weakness/fatigue	Rapid/fast heartbeat

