Numbness/tingling in the lips or tongue	Blurred/impaired vision	Sleepiness
Anger/stubbornness/sadness	Lightheaded/dizziness	Headaches
Nightmares/crying out during sleep	Lack of coordination	Seizures/ Unconsciousness

If a participant reports symptoms of hypoglycemia, instruct them to have their blood glucose level checked if possible:
 
 
• If the blood glucose level is less than the lower limit of normal but <math>\geq 55</math>mg/dL (grade 1 hypoglycemia), instruct the participant to switch to every other day dosing of the study agent. If this does not alleviate the participant's symptoms, instruct the participant to stop taking the study agent.
 
• If the blood glucose level is <math><55</math>-40 mg/dL (grade 2 hypoglycemia), instruct the participant to stop taking the study agent.
 
• If the participant is unable to have their blood glucose checked, base the dose modification on the severity of their symptoms. 
 
○ If the participant is experiencing grade 1 symptoms, and taking the study agent with a more substantial meal has not improved the symptom(s), instruct the participant to switch to every other day dosing. If this does not alleviate the symptom(s), instruct the participant to stop taking the study agent.
 
○ If the participant is experiencing grade 2 symptoms, instruct the participant to stop taking the study agent.
 
 
 
		

*For immediate, short term management of hypoglycemic symptoms, instruct the participant to try one or more of the following:
 
 
• Eat a handful of raisins or candy
 
• Drink a glass of juice, milk, or a regular (non-diet) soda
 
• Eat a small snack
 
		

Jaundice: Discontinue study agent. Do not re-start. Perform liver function tests ASAP.
		

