#### 7.4.2 Physical Exam and Vital Signs

The physical exam will consist of an evaluation of the participant's general state of health and will include at minimum an ENT exam and evaluation of the chest, heart abdomen, and extremities. The presence/absence of edema and signs/symptoms of congestive heart failure will be noted. Vital sign assessment will include temperature and resting (measured after participant has been seated for at least 5 minutes) pulse, respiratory rate and blood pressure. Weight will also be measured. The participant's weight at this visit will be compared to their weight at the baseline visit. If the participant has gained more than 5 pounds since the baseline visit, a more thorough evaluation for signs and symptoms of congestive heart failure should be performed.

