**APPENDIX B: PILL DIARY**

UWI2016-07-01: Phase IIB Randomized, Placebo-Controlled Trial of ACTOplus met® XR in Subjects with Stage I-IV Squamous Cell Carcinoma of the Oral Cavity or Oropharynx Prior to Definitive Treatment	PID#: _____ Date: ___/___/_____
--	------------------------------------

PILL DIARY PAGE 1 of 3			
Dosing Instructions:	
Take one (1) tablet by mouth daily with a meal at approximately the same time each day.
 
Do not chew, cut or crush the tablets.
 
Do not take on an empty stomach.
 
Tablets are moisture and light sensitive. Keep the tablets tightly closed in their original container. Do not transfer to a pill organizer.
 
If you miss a dose, take it with your next meal on the same day. Do not make up a dose by taking two doses in one day.
		
Important Reminders:	Contact study staff immediately if you experience any of the following:		
	Nausea or Vomiting	Loss of appetite	Stomach pain
	Slow or irregular heartbeat	Unusual weakness or tiredness	Unusual muscle pain
	Trouble breathing (especially while lying down)	Swelling in the ankles or feet	Rapid weight gain
	Minimize use of alcohol:		
	Women:	No more than 3 drinks/day or more than 7 in a week.	
	Men:	No more than 4 drinks/day or more than 14 in a week.	
	One drink is:		
	Beer (12 oz.) 1 standard can or bottle	Wine (5 oz.) 1 standard glass	Spirits (6 oz.) 1 mixed drink or one 1.5 fluid oz. shot
	Check with study staff before taking any new medications to be sure the medication is not excluded for use while on this study.		
Notify study staff before having any scans (e.g. CT scan). The study medication should not be taken with the iodine containing dye used for some types of scans.			
Instructions for Completing the Pill Diary:	
Record the date and time you take your dose each day and initial each entry. In the Comments column:
 
 
• List any side effects or symptoms noticed.
 
• List any new medications taken and reason for taking
 
• If you missed a dose indicate why.
 
• Make a note if you've lost any pills
 
• Include any additional information you would like to note.
 
		

UWI2016-07-01: Phase IIB Randomized, Placebo-Controlled Trial of ACTOplus met® XR in Subjects with Stage I-IV Squamous Cell Carcinoma of the Oral Cavity or Oropharynx Prior to Definitive Treatment	PID#: _____ Date: ___/___/____

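### For heart-failure and lactic-acidosis symptoms at Grades 1 and 2, Section 5.6 sets milder default actions than the immediate stop and evaluation in Section 6.2, and the visible text does not say which section governs

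*Combined protocol and SAP*

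**What the plan says.** Section 6.2 describes two rare, serious risks from the boxed warning and lists symptoms for each. Three belong to congestive heart failure: edema, dyspnea, and weight gain that is both rapid and excessive. Five belong to lactic acidosis: abdominal pain, myalgia, malaise, somnolence and respiratory distress. On a report or "finding of any of these symptoms, the participant should be instructed to discontinue taking the study agent immediately and brought in for evaluation". The instruction applies after study treatment begins and has no CTCAE grade or attribution condition. Suspected lactic acidosis is to be managed in hospital.

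Section 5.6 is a grid of grade by attribution. The Grade 1 row, and the Grade 2 cell for unlikely or unrelated events, open with "No modification unless the A.E. is unacceptable to the participant or the physician feels it is in the participant's best interest medically". The Grade 2 cell for related events first asks whether dose timing may be the cause and, if so, suggests another time of day or a larger meal. If timing is unlikely, or the change fails, staff are to "instruct the participant to hold study agent until the AE resolves to" Grade 1 or below, then restart on alternate days. Permanent discontinuation follows only if the event recurs.

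Below the grid are event-specific rows for hypoglycemia and jaundice. The jaundice row reads "Discontinue study agent. Do not re-start. Perform liver function tests ASAP". Neither boxed-warning condition has a row.

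The visible references to Section 6.2 are descriptive. Section 5 opens with "Reported AEs and potential risks are described in Section 6.2", and Section 11 refers to it as a list of adverse events.

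**The concern.** Staff who take a call about mild new ankle swelling or muscle pain would naturally turn to the section on dose modification. Followed as written, its default keeps the participant on drug. Section 6.2 asks for a stop and an evaluation for the same report. Which of these happens could depend on which section the staff member has open.

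The rest of the visible protocol does not close the gap during dosing. The only scheduled adverse-event assessment before the end of study is the Day 5-7 telephone call (Section 7.3.1). The pill diary in Appendix B tells participants "Contact study staff immediately if you experience any of the following" and lists breathing trouble, swelling, rapid weight gain, muscle pain and stomach pain among the prompts. It does not tell them to stop taking tablets. The one other written trigger for a heart-failure work-up is in Section 7.4.2: for anyone who "gained more than 5 pounds since the baseline visit, a more thorough evaluation for signs and symptoms of congestive heart failure should be performed". That check is made at the end-of-study visit, and Section 5.2.5 puts the final dose on the day before the end-of-study surgery or biopsy.

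What is at stake is prompt recognition of two serious drug risks in individual participants, not the efficacy comparison.

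**Working it through.** The plan states no figure on this point, so the check sets the two sections side by side.

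**Symptoms in Section 6.2.** 3 (heart failure) + 5 (lactic acidosis) = 8. None carries a CTCAE grade. Two carry severity in their wording: the weight gain must be excessive and rapid, and respiratory distress is not a mild term. The other six (edema, dyspnea, malaise, myalgia, somnolence, abdominal pain) are unqualified.

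**Combinations in Section 5.6.** Grades 1 and 2 × two attribution classes = 4. The Grade 1 row appears in the extracted text as one cell that seems to span both attributions.

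| Grade and attribution | Default in 5.6 | Discretion clause opening the cell? | Does the default meet 6.2? |
|---|---|---|---|
| 1, unlikely or unrelated | No change | Yes | Only if discretion is used |
| 1, related | No change | Yes | Only if discretion is used |
| 2, unlikely or unrelated | No change | Yes | Only if discretion is used |
| 2, related | Timing or meal change if timing may be the cause; otherwise hold, then alternate days | No | Timing branch: no stop. Hold branch: a stop, but no evaluation, and restart depends on resolution alone |

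So three of the four combinations default to no change and can be reconciled with 6.2 through discretion. The fourth cannot be reconciled by its own wording. Its timing branch continues the drug, and its hold branch omits the evaluation. Section 6.2 leaves one point open here: it does not say whether the stop is permanent or lasts only until the evaluation, so the alternate-day restart may or may not fit it.

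The Grade 3 cells already hold the agent pending consultation or discontinue it, so the difference lies in the lower grades.

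**Precedence.** The references in Sections 5 and 11 do not rank the two sections, and the rows under the grid cover only hypoglycemia and jaundice. No visible statement settles the order.

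**The case against.** The strongest reply is that there is no conflict of orders. A physician who stops the drug because Section 6.2 says so is acting in the participant's medical interest, which 5.6 expressly permits. Section 6.2 is also the more specific rule and concerns boxed warnings, so reading it over a general grid is natural. This stands for three of the four combinations. A reader might infer that the two sections give opposite instructions throughout; the documents do not support that. The reply does not reach the Grade 2 related cell, which has no such clause, and the protocol nowhere states the specific-over-general reading.

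A second reply is that safeguards exist elsewhere. Section 11.1.5 requires clinically appropriate follow-up of adverse events, and Sections 7.3.1 and 7.4.5 require a physician's attribution for each one. Section 14.2.7 requires a signed acknowledgement of the brochure or package insert. Sections 4.1.9 and 4.2 exclude a history of heart failure or liver disease, excess alcohol use, limb edema above Grade 1 and an eGFR of 45 mL/min or less. Dosing lasts at most 25 days. These lower the chance that a symptom goes unassessed, but they do not say which section governs. It would be wrong to infer that no evaluation would take place; the evaluation step is missing only from the table cell.

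A reader might also see a second clash in the hypoglycemia row, which lists fatigue and sleepiness and can lead to alternate-day dosing for mild symptoms when glucose cannot be checked. Section 6.2 names neither term. Equating them with malaise and somnolence is interpretation, and the documents do not support treating that row as part of the problem.

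Finally, stopping at any grade may be too strict for some symptoms. Section 6.2 itself reports abdominal discomfort in 6.4% on metformin against 4.8% on placebo, and a meal change may suit a mild case. That is a fair clinical argument for narrowing Section 6.2, but as written it already asks for the stop.

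**Conclusion.** The point holds as a divergent default between Sections 5.6 and 6.2 at Grades 1 and 2, with no visible rule of precedence. In three of the four combinations discretion can reconcile the sections. In the Grade 2 related cell the written actions fall short of Section 6.2.

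The size is modest. The documents do not allow a frequency estimate: no symptom rate is split by grade, and nothing shows which section staff would follow. For example, the 5.8% edema rate that Section 6.2 gives for 30 mg pioglitazone with metformin is not graded and does not come from a 10-21 day exposure. Low frequency is a judgement from the exclusions and the short dosing period. No effect on power, type I error or the Ki-67 analysis is claimed.

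The conclusion rests on the visible text only. Consent pages were removed, and the Visit Guides mentioned in Section 12.3 were not available; either might contain a relevant instruction.

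**What to change.** Add one row to the 5.6 table, beside the hypoglycemia and jaundice rows:

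*New or worsening symptoms of congestive heart failure or lactic acidosis listed in Section 6.2, any grade or attribution: Section 6.2 takes precedence over this table. Stop study agent immediately and bring the participant in for evaluation; re-start only on the advice of the medical monitor.*

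Add a note that stable baseline Grade 1 edema, which Section 4.2.13 allows at entry, is not a trigger unless it worsens. Do not extend the row to the fatigue or sleepiness terms in the hypoglycemia row, since that would go beyond Section 6.2. The stop and evaluation are already required there; the re-start clause settles what 6.2 leaves open.

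The cost is a wording amendment, which under Section 14.3 needs DCP approval and then CIRB approval before it takes effect, plus a site memo. No scheduled visits or participants are added. A few more doses may be interrupted. Under the 80% rule in Section 5.7.1:

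- 10 doses: 0.80 × 10 = 8 needed, so 2 may be missed.
- 21 doses: 0.80 × 21 = 16.8, so 17 needed and 4 may be missed.
- 25 doses: 0.80 × 25 = 20 needed, so 5 may be missed.

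A longer stop would fall below that threshold, although Section 13.6 includes all participants with evaluable paired samples in the biomarker analysis.

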### **6.3 Availability**

Blinded ACTOplus met® XR (pioglitazone and metformin hydrochloride extended-release) tablets (Takeda Pharmaceuticals America, Inc., Deerfield, IL) with 30 mg and 1000 mg of agents, respectively, is an investigational agent supplied by NCI, DCP. Blinded matching placebo tablets will also be supplied by NCI, DCP. These agents will be distributed through the DCP Repository, MRIGlobal.

